Visit#6: Follow-up (one month); END of STUDY.

Study Population: Sixty-five non-treatment-seeking, alcohol-dependent participants will be recruited. Fifty-eight participants will be enrolled for screening with **50 participants (n = 50)** expected to complete the study. Participants will primarily be recruited via advertisements placed in local newspapers and posted on buses.

Safety Measurement/Parameters: Risks of medication side effects will be minimized through careful and detailed screening of participant. Signs of anxiety and stress, adverse events and vital signs will be assessed at each visit by psychometric assessments. Safety laboratory tests will be evaluated at baseline, and at the end of the study participants will receive a behavioral motivational session at the end of Visit 5.

Financial considerations: There will be no cost(s) to participate in this study. The study medications and all procedures that are not part of routine care, but are required for the study, will be provided to the participant. If eligible for the study, participants will receive \$25 for the randomization visit (Visit# 2) and for the follow-up visits (Visits #4 and #6). During the laboratory phase, at each visit (Visits #3 and #5) participants are compensated \$100 + another possible \$3/drink as incentive for not drinking (max \$24). Therefore, each participant may be compensated up to \$323 during the entire study period. Participants will be also compensated for their travel costs.

Specific Aims:

Aim 1: to assess the safety and tolerability of mifepristone and yohimbine while consuming alcohol.

Aim 2: to test the hypothesis that an increase in alcohol craving induced by yohimbine is antagonized by pre-administration with mifepristone.

Aim 3: to test the hypothesis that an initial priming drink and alcohol consumption induced by yohimbine is antagonized by pre-administration with mifepristone.

TABLE OF CONTENTS

PROTOCOL SYNOPSIS	2
TABLE OF CONTENTS	3
SPECIFIC AIMS	4
RATIONALE AND SIGNIFICANCE TO THE ALCOHOL FIELD	5
Stress and alcohol dependence	5
Clinical relevance	5
Pharmacological stress targets	5
Mifepristone	5
Stress-induced models	6
Integration: psychoneuroendocrinology and trauma factors	6
Significance for NIAAA	6
Innovation	6
The Investigator Team	7
The qualified medical personnel during the laboratory sessions	7
RESEARCH DESIGN AND METHODS	8
Overview of Proposed Research	8
Medications and Doses	8
Study Procedures	9
Data Analysis Plan	10

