Visit 1 (Screening). All procedures and responsibilities of each member of the research team are described in Appendix Z (page 1). Following a breath analyzer (BrAC) that must be 0.00, participants will then be assessed on demographics, medical history, physical examination, vital signs and ECG. Blood, urine, cortisol and clinical assessments are performed to screen individuals for inclusion/exclusion criteria and monitor adverse effects; we will collect a baseline salivary cortisol sample (three samples by spitting in a tube) and administer psychometric assessments. The salivary cortisol samples will be stored in [name] lab. A study physician will administer the Brief Trauma Questionnaire (BTQ, Appendix J). After a study physician reviews and approves the medical history and lab results, the participants will be called with the results and scheduled for Visit 2. When the RA or [name] administers the SCID, Drs. [name] will review the SCID the screening day. They will review the rest of the other blood, saliva and urine laboratory analysis before enrolling any participant in the study. Session will last approximately 3-4 hours. *Randomization will be performed on Visit 2.*

Visit 2 (Randomization): All procedures and responsibilities of each member of the research team are described in Appendix Z (page 2). BrAC = 0.00 before initiating any procedure; participants in addition to the psychometric assessments (see complete list in Appendix Z) they will then be assessed for life trauma exposure. We will assess lifetime history of trauma exposure using Life Events (LEC) and Post Traumatic Stress Disorder (PTSD) (PCL) Checklists. The participants will then be randomized and we dispense the study medication (see Appendix Z). The overall descriptions of the measures and the specific questions and responses that may trigger a call to the licensed clinician are provided in the Protection of Human Subject section. *Compensation:* sessions will last approximately 3 hours, and subjects will receive \$25 for participation.

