NOTE - Suicidality: To assess the risk of suicidality we included the Suicide Assessment Five-Step Evaluation and Triage (Appendix K). It is a 5-step screening tool developed in collaboration with the Suicide Prevention Resource Center and Screening for Mental Health. This assessment will be done by the study physician during screening (see Appendix Z for assessments schedule).. Also, the HAM-D question # 3 is about suicide; if participants score >0 during the course of the trial, we will alert [name] immediately.

Screening and Randomization: Potential participants will be screened by telephone using a standardized questionnaire, which includes alcohol use, personal medical/mental health history and the major inclusion/exclusion criteria for the study. Eligible participants will receive information of the logistics (duration, commitment, compensation, measures) and on the medications that will be administered in the study. Interested volunteers are asked to come for a comprehensive visit at CAAS. At screening, **subjects must have their BrAC measured (must be = 0.00), and must be = 0.00 every time before initiating any procedure at every visit.** During this visit, participants will be assessed using Inclusion/Exclusion criteria (Table 1), psychometric scales (Appendix Z), vital signs, ECG, blood (two tubes) and urine analysis; three samples of salivary cortisol will also be collected (by spitting tube) to measure cortisol level. All participants

will undergo careful medical and psychiatric assessment and must meet all inclusion and no exclusion criteria to qualify for this study.

Table 1 – Inclusion and Exclusion Criteria

Inclusion

- Male or female, 21 to 65 years of age
- Females must be postmenopausal for at least one year or surgically sterile (proven by medical record)
- **Meet criteria for Alcohol Use Disorders (AUD) DSM-5 diagnosis**
- Meet criteria for heavy drinking (≥ 35 drinks/week for men; ≥ 28 drinks/week for women)
- Must be in good health as confirmed by medical history, physical examination, ECG, lab tests
- Participants must be willing to take oral medication and adhere to the study procedures
- Breath alcohol (BrAC) = 0.00 at each visit
- Be able to understand informed consent and questionnaire in English at an 8th grade level

Exclusion

- Individuals expressing interest in treatment for alcoholism
- Premenopausal women
- Participants who have significant alcohol withdrawal symptoms, defined as a CIWA-Ar score ≥ 7

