- A repeated positive urine drug screen at baseline for any illegal substance except marijuana.
- Individuals diagnosed with a current “severe” Substance Use Disorder (SUD) diagnosis, other than alcohol or nicotine
- Meet DSM-5 criteria for a diagnosis of schizophrenia, bipolar disorder, or other psychoses
- An active illness within the past six months of the screening visit that meets the DSM-5 criteria for a diagnosis of Major Depressive Disorder (MDD) or Anxiety Disorder, or history of attempted suicide
- Clinically significant medical abnormalities: unstable hypertension, clinically significant abnormal ECG, bilirubin $>150\%$ of the upper normal limit, ALT/AST $>300\%$ the UNL, creatinine clearance ≤ 60 dl/min
- Current use of psychotropic medications that may have an effect on alcohol consumption
- Current use of any medication involved in the metabolism of alcohol such as aldehyde dehydrogenase (ALDH), alcohol dehydrogenase (ADH) and CYP2E1: Cefamandole, Cefotetan, Sulfamethoxazole, Nitroglycerin, Chlorpropamide, Glyburide.
- Current use of any medication (CYP3A4 inhibitor and substrate) that may interact with mifepristone: cyclosporine, fentanyl, heparin, escitalopram, lovastatin, simvastatin, warfarin
- Current use of any medication (CYP2D6 inhibitor and substrate) that may interact with yohimbine: amitriptyline, doxepin, nortriptyline, venlafaxine
- Medical contraindications for use of mifepristone or yohimbine
- A history of adverse reaction or hypersensitivity to mifepristone or yohimbine
- History of suicide
- History of seizure disorders
- Hypokalemia (low potassium level) <3.5 mEq/L
- Participated in any behavioral and/or pharmacological study within the past **30 days**
- Neuroendocrine disorders
- Taking corticosteroids
- Bleeding disorders
- Pre-existing QT prolongation on ECG
- History of porphyria (Mifepristone progesterone receptor antagonist is an inducer of CYP-450 and therefore may have the ability to precipitate or exacerbate attacks of acute porphyria)
- Not willing to engage in protected sex (condom). **This risk includes both women and men.** Mifepristone long half-life ($t_{1/2} = 18$ hrs) and its three main metabolites retain considerable affinity toward human progesterone and glucocorticoid receptors, with serum level similar to the parent mifepristone and there

are no studies on the presence of mifepristone or metabolites in semen

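### The creatinine clearance exclusion in Table 1 is printed in dl/min; read literally it excludes everyone and cannot separate impaired from normal renal function, so the unit needs to be confirmed and corrected.

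*Protocol*

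**What the plan says.** The exclusion half of Table 1 in the protocol has an item that begins "Clinically significant medical abnormalities: unstable hypertension, clinically significant abnormal ECG" and goes on to numeric limits for bilirubin, for ALT/AST and for renal function. The renal limit is "creatinine clearance ≤ 60 dl/min".

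The Screening and Randomization section, just above the table, says how the criteria apply: participants "must meet all inclusion and no exclusion criteria to qualify for this study". One exclusion met is enough to make a person ineligible.

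Three other statements bear on the point:

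- The inclusion half of Table 1 has a general health requirement: "Must be in good health as confirmed by medical history, physical examination, ECG, lab tests".
- Under Study Procedures, Visit 1 (Screening), the study physicians' duties include this: "They will review the rest of the other blood, saliva and urine laboratory analysis before enrolling any participant in the study".
- The synopsis, under Study Population, gives 50 participants as "expected to complete the study".

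No other place in the protocol or SAP text gives a creatinine clearance, a renal limit or a normal range.

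**The concern.** An eligibility threshold has to divide volunteers into those who may enter and those who may not. With the unit as printed, the renal limit lies far above any clearance that a laboratory would be expected to report, so everyone falls on the excluded side and the line gives staff no usable cut-off.

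This is operative text. Eligibility is applied and audited against Table 1, and the neighbouring limits for bilirubin, ALT/AST and potassium are evidently meant to be used as numbers. Safety and tolerability are the trial's first aim, and the synopsis relies on careful screening to limit medication risk. The protocol's only numeric renal criterion should therefore be one that staff can apply without guessing at the unit.

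**Working it through.** The threshold is a chosen cut-off with no inputs behind it, so there is no planned figure to reproduce. The check is a unit conversion followed by application of the printed rule.

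**Inputs**

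- Threshold: 60 dl/min, with values at or below it excluded (Protocol, Table 1, Exclusion).
- Rule: any one exclusion makes a volunteer ineligible (Protocol, Screening and Randomization).
- Expected completers: 50 (Protocol, synopsis, Study Population).
- Conversion: 1 dl = 100 ml (definition of the unit).
- Clearance values to test: 15 to 500 ml/min. This is an assumption, made wide on purpose because the documents give no range.
- Normal adult range, for scale only: 80 to 130 ml/min. This is also an assumption.

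**Step 1. Convert the limit.** 60 dl/min × 100 ml/dl = 6,000 ml/min = 6 L/min. Over a day, 6 × 1,440 = 8,640 L.

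**Step 2. Apply the printed rule.**

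| Assumed clearance (ml/min) | In dl/min | At or below 60 dl/min? |
|---|---|---|
| 15 | 0.15 | yes, excluded |
| 30 | 0.30 | yes, excluded |
| 60 | 0.60 | yes, excluded |
| 90 | 0.90 | yes, excluded |
| 120 | 1.20 | yes, excluded |
| 200 | 2.00 | yes, excluded |
| 500 | 5.00 | yes, excluded |

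Even the top of the range is well inside the excluded region: 60 / 5.0 = 12, so the limit is 12 times the largest value tried.

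**Step 3. Put the limit on a familiar scale.** The assumed normal range is 0.8 to 1.3 dl/min. 60 / 1.3 = 46 and 60 / 0.8 = 75, so the printed limit is about 46 to 75 times an assumed normal clearance. Step 2 does not depend on this range.

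**Step 4. Compare with the recruitment plan.** Steps 1 and 2 with the binding rule imply that nobody qualifies. The synopsis expects 50 people to complete. The two statements cannot both hold, so the threshold cannot have been meant as printed.

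**Step 5. Look for a correction elsewhere.** The good-health criterion refers to laboratory tests without naming a renal value. Visit 1 provides for review of blood and urine results without naming one either. Nothing in the available text restates the limit in another unit.

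**The case against.** The strongest reply is that this is one letter in one line, and that nobody would act on it literally. A physician reading a laboratory report would see that the unit is impossible, and the protocol's own recruitment figures show that a rule barring everyone was not intended. The number 60 is stated and only its unit is in doubt. Other screening remains, through the good-health criterion and the laboratory review before enrolment. No endpoint, sample size, alpha or analysis is touched. All of this stands, and it is why the practical impact is minor.

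Two further cautions are fair. The text used here was extracted from a PDF, and at least one character in the SAP was lost that way (the alpha symbol in its closing paragraph). The line in Table 1 reads cleanly and is neither redacted nor broken, but the source page should be checked. Appendix Z, which the protocol cites for visit procedures, is not in the text either, so a correct figure there cannot be ruled out.

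A reader might draw stronger conclusions that the documents do not support:

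- **That nobody is screened for renal impairment.** A rule that excludes everyone also excludes people with impaired function. Its fault is that it does not discriminate, and the two general provisions remain.
- **That every participant enrolled is a protocol deviation.** This follows only from a literal reading that the 50 expected completers contradict.
- **That a particular renal hazard of the study drugs goes unguarded.** No passage links renal function to risk from mifepristone, yohimbine or alcohol. The section on drug-drug interactions discusses metabolic enzymes.

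The objection does not remove the error. The two backstops contain no renal number, so they cannot stand in for the threshold. Where the intended unit is left to inference, staff must supply it themselves.

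**Conclusion.** Wrong as written, as a decision threshold, with minor practical impact. The printed limit equals 6,000 ml/min, excludes every value in an assumed range of 15 to 500 ml/min, and so cannot distinguish impaired from normal renal function. Taken with the rule that no exclusion may be met, it contradicts the 50 expected completers.

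The conversion is exact. That everyone is excluded rests on the assumption that no volunteer's clearance exceeds 6,000 ml/min; the narrower normal range serves only for scale. That the line is a slip in the unit is an inference from the recruitment plan, because the documents do not state the intended unit. This review does not say which threshold is right.

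**What to change.** The sponsor should check the creatinine clearance line against the source document or the IND file, confirm the intended value and unit, and correct Table 1. The corrected criterion should then be used wherever eligibility is checked, including Appendix Z if the limit is repeated there. The choice of threshold is for the sponsor, and none is proposed here.

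The cost is a correction to one line of Table 1. It adds no procedure or visit and changes no analysis.

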Assessments and Breach of Confidentiality: There is always some risk that participants will be identified as participants in a study or that clinical assessments will involve questions on illegal behaviors, or will adversely affect participants' well-being; while this does present a confidentiality risk, studies have been performed in the open public without evidence of participant harm. Inadvertent breach of confidentiality concerning drinking behavior is also a risk. All data will be used for research purposes only, and will not be revealed without the participant's written consent. Data will be kept in a secure locked file in the locked study office. Data will be entered into a computer database at the study site, which is password protected involving only numerical identifications that can only be linked with subjects' identification locked in a cabinet known only to the research staff. Access to data will be available only to investigators involved in the study. The research staff is trained in confidentiality procedures. As an additional layer of security, we will use a "Subject Number" from a Log and keep contact information in a separate locked location.

We will apply for a **Certificate of Confidentiality** issued by the National Institutes of Health to protect identifiable research information from forced disclosure. The certificate will allow those of us who have access to research records to refuse to disclose identifying information on research participants in any civil, criminal, administrative, legislative, or other proceeding, whether at the federal, state, or local level. By protecting us and Brown University from being compelled to disclose information that would identify research subjects. A Certificate of Confidentiality helps achieve the research objectives and promote participation in studies by helping to assure confidentiality and privacy to our participants.

Coercion: Risks of coercion are minimized by having participation payments be reasonable for the amount of time and effort required and comparable to other studies in this area. The likelihood of financial coercion is low because the compensation is commensurate with the amount of time and effort required for this study. There will be no cost(s) to participate in this study. The study medications and all procedures that are not part of routine care, but are required for the study, will be provided to the participant. If eligible for the study, participants will receive \$25 for the randomization visit (Visit# 2) and for the follow-up visits (Visits #4 and #6). During the laboratory phase, at each visit (Visits #3 and #5) participants are compensated \$100 + another possible \$3/drink as incentive for not drinking (max \$24). Therefore, each participant may be compensated up to \$323 during the entire study period. Participant will be also compensated for their travel costs. Participation fees and transportation expenses will have been approved by the Brown University IRB. There will be no other inducements.

Alcohol withdrawal: Since participants must have BrAC = 0.00 before initiating any procedure, there is risk of withdrawal syndrome. Our experience across numerous alcohol studies suggests that the risks for withdrawal from alcohol are minimal in this study as any potential participant with a CIWA ≥ 7 or having

significant hepatic dysfunction (by blood laboratory analysis) will be excluded during screening. As a result of our screening we can recruit people who drink enough to qualify for this study yet don't drink at a level that would potentially put them at risk for withdrawal. Alcohol craving following yohimbine administrations are reported to be modest, but significantly higher than placebo, however with not increased anxiety ratings. Alcohol craving will be monitored by psychometric scales. However, it is still possible that some participants may experience some withdrawal symptoms if they stop or reduce their drinking on their own. These symptoms may become severe enough to require hospitalization in order to be managed safely. Again, any participant with a CIWA score ≥ 7 (agitation, tremor, sweats) at any time will be excluded from the study and immediately referred for medical attention at a Hospital Emergency Room or mental health clinic. Compliance: We will use a modified Medical Management (MM) used by the COMBINE study that has been revised and tailored for this study¹⁰⁷. The use of these components of MM in this study is aimed to facilitate participant adherence to pharmacotherapy. Sessions are conducted by trained research staff.. We will be dispensing the medication or placebo in blister packs to facilitate compliance. The initial session will be 30-45 minutes in order to establish rapport and will include a discussion of how the medications work, discussion of potential side effects and what to do about them, and a motivational interviewing-oriented discussion related to medication adherence, including the participant's experience with medications compliance, when and why they might miss doses, and what mechanisms could be useful to enhance medication adherence. Another important part of the MM is the focus on alcohol-related medical problems (such as liver panel exam).

Medications and Drug-Drug Interactions: Corcept Therapeutics will provide mifepristone (600 mg, for seven days plus three extra day doses) or matching placebo. Participants will receive a blister pack containing 10 capsules of mifepristone or placebo (7 days + three extra doses). Participants will return for the first follow-up visit and they will receive the additional blister pack. Bayview pharmacy will provide yohimbine (32.4 mg) formulated in a single capsule that will be administered at CAAS under team supervision prior to the alcohol laboratory session. Risks of medication side effects will be minimized through careful and detailed screening of participants *by the PI ([name])* to minimize recruitment of those who might be at higher risk for adverse events, as well as careful and detailed monitoring of adverse events and participant well-being during the study.

Mifepristone: Since mifepristone is a FDA-approved oral medication for the termination of early pregnancy, we will exclude women with childbearing potential regarding the birth control methods used. The following complications or risks have been reported, are known, or may occur with mifepristone: the most commonly reported side effects associated with the use of mifepristone include: abdominal or stomach pain, back pain, diarrhea, dizziness, headache, nausea or vomiting. Other less common side effects associated with the use of mifepristone include: cough, fainting, fever, heartburn, indigestion, lack of strength, or stomach discomfort. Rare side effects associated with the use of mifepristone include: sleepiness, pain during sexual intercourse, pale skin, shaking chills, shortness of breath, stuffy or runny nose, and unusual bleeding or bruising. Mifepristone may cause low blood potassium (hypokalemia); symptoms may include muscle weakness, aches, or cramps, or abnormal palpitations. Subjects with low potassium levels at screening will be excluded. In eligible participants, hypokalemic symptoms will be monitored during the entire study. Mifepristone progesterone receptor antagonist is an inducer of CYP-450 and therefore may have the ability to precipitate or exacerbate attacks of acute porphyria (exclusion criteria).

Because mifepristone has been used safely for termination of early pregnancy by the FDA since September 2000 at doses of 600 mg (single dose), we considered mifepristone titration in our study (one week therapy); however, mifepristone has been used at 600 mg dose in other clinical research studies and is currently being evaluated by Corcept Therapeutics in conducting studies using a similar dose including: control of hyperglycemia secondary to hypercortisolism in adults with endogenous Cushing's syndrome who have type 2 diabetes mellitus or glucose intolerance and have failed surgery or are not candidates for surgery. Additionally, Corcept Therapeutics is engaged in the discovery, development and commercialization of drugs for severe metabolic, psychiatric and oncologic disorders. Current trials include: Metastatic Triple Negative Breast Cancer (phase I), A Study of Mifepristone vs. Placebo for individuals With Major

Depression With Psychotic Features (phase III) and Mifepristone in Children With Refractory Cushing's Disease in collaboration with National Institute of Child Health and Human Development.

It will be stated clearly in the consent form and to the participants verbally, that participants must engage in protected sex (i.e. wear a condom). This risk includes men and women. Mifepristone has a long half-life ($t_{1/2} = 18$ hrs); its three main metabolites retain considerable affinity toward human progesterone and glucocorticoid receptors, with serum levels similar to the parent mifepristone and there are no studies on the presence of mifepristone or metabolites in semen. This will be clearly spelled out in the consent form document

Yohimbine: The oral dose of yohimbine for this study is based on prior studies in which yohimbine was administered to examine neuroendocrine probe in human studies. Ample data support the safe use of yohimbine to induce craving in alcohol-dependent individuals, and the safe induction of stress in PTSD veterans and gamblers. In this study, yohimbine (32.4mg) is administered below the therapeutic index to a dose considered dangerous (>100mg). Furthermore, yohimbine will be administered only once, during the laboratory session and under direct supervision of the study personnel. It will be given at a safety-tested dose to increase noradrenergic activity already being evaluated in psychiatric individuals with clinically relevant stress conditions such as PTSD, anxiety, and depression. Finally, yohimbine's short half-life ($t_{1/2} = 1-2$ hour) provides a transient effect. The protocol includes close monitoring of blood pressure, heart rate, and cortisol levels by [name] or research laboratory staff, and we have [name] on call. In addition, the Hamilton Anxiety Rating Scale (HAM-A) (Appendix O), Self-Evaluation Questionnaire for state (STAI-y1) and Self-Evaluation Questionnaire for trait (STAI-y2) (Appendix R and S) to assess and compare anxiety at baseline and prior to releasing the participants after laboratory session are included in the assessments (**Appendix Z**). If anxiety is higher at the end of the study we will call [name] to have him meet with the participant before release. The most common side effects reported by the use of yohimbine are: an allergic reaction, irregular or fast heartbeat, confusion, dizziness, anxiety, irritability, or nervousness, tremor, headache, skin flushing.

Drug-drug interactions: To reduce risk of drug-drug interactions, participants will be instructed to call our study team before taking any new prescription or over-the-counter medication. Participants will be asked to avoid taking medications that could interact with mifepristone and yohimbine. A wallet card identifying themselves as participants in a study receiving mifepristone and yohimbine (single dose) will be provided. This card will also contain the contact numbers of our study team, including emergency numbers of the PI and study physicians on call 24 hours a day (**Appendix X**). Participants will be asked to carry this card that will, in case of emergency, alert the medical personnel treating the participants that they may be taking mifepristone. This card, which should be kept at all times, will also include appropriate drug information and precautions.

As this project is guided by [name] neuroscience pre-clinical work, she did not observe any **two-way drug interactions** in preclinical models when administering the combination of mifepristone (systematically and by brain microinfusion into the central nucleus of the amygdala) and yohimbine⁴⁷.

Moreover, pharmacokinetically, yohimbine and mifepristone do not share liver microsome metabolic pathways; yohimbine is metabolized by CYP2D6, and mifepristone via CYP3A4. In [name] preclinical models, she did not observe any **three-way drug interactions** when administering the combination of mifepristone, yohimbine, and alcohol. The primary enzymes involved in the metabolism of alcohol are aldehyde dehydrogenase (ALDH), alcohol dehydrogenase (ADH) and CYP2E1. Pharmacodynamically, both mifepristone and yohimbine do not show the CNS depressant properties of alcohol and we should not expect increased sedation or depression of respiratory and/or cardiac functions. [name] has pharmacy background and they will include: 1) a search using Lexicomp, and 2) systematic symptom monitoring of drug-drug interactions between yohimbine, mifepristone and alcohol. While we recognize that both drugs, as well as alcohol, have indirect adverse effects, we note that [name] have experience in administering multiple drugs (ariPIPrazole with topiramate at clinical doses) and alcohol. Their experience suggests that without direct interactions, the side effects from both drugs may be broader but not additive with each other. *Finally, we have already obtained the Investigational New Drug*

(IND#121984) from FDA that determined that the clinical investigation of mifepristone and yohimbine while consuming alcohol is safe to proceed. In addition, our IND was cross-referenced by the IND of Corcept Therapeutics (IND#059737) for chemistry, manufactory, pharmacological, and toxicology data of mifepristone. Participants will receive detailed information on the study medication, including its current use and possible side effects.

The following medications are contraindicated with mifepristone: antithrombin alfa, antithrombin iii, argatroban, aspirin, bemiparin, bivalirudin, budesonide, cisapride, clobetasone, cortisone, cyclosporine, dabigatran, dalteparin, deflazacort, dexamethasone, dihydroergotamine, dronedarone, enoxaparin, ergotamine, fentanyl, fludrocortisone, fondaparinux, heparin, hydrocortisone, lepirudin, lovastatin, methylprednisolone, phenindionem, pimozide, prednisolone, prednisone, protamine, quinidine, simvastatin, sirolimus, tacrolimus, thioridazine, tinzaparin, triamcinolone, warfarin.

The following medications are contraindicated with yohimbine: amitriptyline, doxepin, nortriptyline, venlafaxine

The following medications are contraindicated with alcohol: cefamandole, cefotetan, sulfamethoxazole, nitroglycerin, chlorpropamide, glyburide.

The most common medications are listed in the emergency card and in the consent form.

Drug Storage and Accountability. The investigator will ensure that all study drugs are stored in a secured area under recommended storage conditions and in accordance with applicable state regulatory requirements in a locked closet in a room accessible only by a card-activated lock.

Mifepristone and yohimbine administration: The use of mifepristone and yohimbine in these studies will be under FDA-approval via IND#121984 ([name] is the IND holder). Only healthy individuals will be eligible for enrollment. Medications will be prepared by Bayview Pharmacy. Females with childbearing potential are excluded regardless of the birth control method adopted, unless the woman has had a surgical sterilization. Participants will be monitored by [name] or research laboratory staff for symptoms of adrenal insufficiency (weakness, nausea, fatigue, and hypotension) that may result by mifepristone administration and increasing BP and HR that may result from the adrenergic effect of yohimbine. [name] will be alerted immediately if any adverse effect arises during the entire study duration. [name] will determine if a participant is in need of hospitalization or other mental health intervention.

Alcohol Cue-reactivity (CR) and Alcohol Self-Administration (ASA) Sessions: The PI will schedule Visit #3 and Visit #5 (alcohol laboratory sessions) only if [name] will be in proximity of CAAS laboratory. The PI will not schedule Visit #3 and Visit #5 if both study physicians are traveling or not in Providence. To assess for medical/psychiatric conditions requiring an intervention, all participants will be evaluated at the end of each laboratory session and at follow-up visits. Individuals will be referred for further evaluation and treatment should any medical/psychiatric conditions occur. Participants are selected for the study and monitored carefully throughout the alcohol laboratory session; should a participant display an adverse effect, [name] will be called immediately. [name] will determine if a participant is in need of hospitalization or other mental health intervention.

Adverse Events

We included the list of side effects and occurrence associated with the two study drugs administered separately.

Side effects and occurrence with study medications	
Mifepristone	Yohimbine
Abdominal pain, cramping (96%)	Anxiety
Uterine cramping (83%)	Irritability
Nausea (43-61%)	Headache
Headache (2-31%)	Sweating
Vomiting (1-26%)	Nausea

Diarrhea (12-20%) Dizziness (1-12%) Fatigue (48%) Nausea (48%) Headache (44%) Endometrial hypertrophy (38%) Hypokalemia (34%) Arthralgia (30%) Vomiting (26%) Peripheral edema (26%) Hypertension (24%) Dizziness (22%) Decreased appetite (20%) Abnormal thyroid test (18%) Xerostomia (18%) Back Pain (16%) Dyspnea (16%) Myalgia (14%) Pain (14%) Sinusitis (14%) Nasopharyngitis (12%) Extremity pain (12%) Diarrhea (12%)	Tachycardia Priapism Worsening of panic attack The frequency not defined
---	---

Adverse Effects: Adverse events (AEs) will be recorded and tracked for this protocol and will be reported to Brown University IRB and FDA. At the follow-up visit, AEs will be recorded and followed to resolution only if they are serious or unexpected, or if the study physician assesses them to be clinically significant. In accordance with FDA reporting requirements, all AEs occurring during the course of the study will be collected, documented, and reported by the investigators. The occurrence of AEs will be assessed starting on the day of randomization.

Unexpected Adverse Events: An unexpected AE is one that is not described with respect to nature, severity, or frequency in the current protocol.

Serious Adverse Events (SAEs): Each adverse event or reaction will be classified by a study physician as being serious or non-serious. Based on the seriousness of the adverse event or reaction, appropriate reporting procedures will be followed. The Code of Federal Regulations Title 21 part 312.32 and International Conference on Harmonization (ICH) Guideline for Industry: Clinical Safety Data Management: Definitions and Standards for Expedited Reporting, ICH-E2A March 1995, as implemented by the U.S. Food and Drug Administration, defines a SAE or serious adverse drug experience as any untoward medical occurrence at any dose that:

- results in death
- is life-threatening; (NOTE: The term "life-threatening" in the definition of "serious" refers to an event in which the subject was at risk of death at the time of the event; it does not refer to an event which hypothetically might have caused death if it were more severe)
- requires hospitalization or prolongation of existing hospitalization
- results in persistent or significant disability/incapacity; or
- is a congenital anomaly/birth defect

In addition, important medical events that may not result in death, be life-threatening, or require hospitalization may be considered a serious adverse drug reaction, when based on appropriate medical

judgment that may jeopardize the subject and may require medical or surgical intervention to prevent one of the outcomes listed in the above definition. If a study subject withdraws from the study or if an investigator decides to discontinue the subject from the study because of an SAE (assessed by the Side Effect Reporting Form (Appendix Q), the subject must have appropriate follow-up medical monitoring including, if necessary, hospitalization. The research laboratory staff will continue to monitor by contacting the participant (phone) until the problem prompting hospitalization has been resolved or stabilized with no further change expected or is discovered to be clearly unrelated to study medication or progresses to death.

Unexpected and Serious Adverse Events Reporting: Any Unexpected or SAE, including death due to any cause, which occurs to any subject from the time of admission through discharge whether or not related to the investigational product, will be reported within 24 hours of knowledge of the event to our local IRB and to the Project Officer of this project via fax or phone call.

Detailed written documentation for all SAEs/unexpected AEs will be submitted **within seven (7) days** to our Brown IRB. Required documents that must be submitted include the following information:

- title of protocol
- description of the unanticipated adverse event
- a determination of whether the event was related to the research study
- name of the drug
- where and when the event occurred
- to whom else the event has been reported

Upon receipt of a notification of an unanticipated adverse event or death, the IRB will determine whether further investigation of the event is required. Depending on the circumstances, the investigator may be required to suspend the study pending the outcome of an IRB review. Also, the IRB may require modification of the risks section of the consent form. These documents may be submitted by facsimile, as e-mail attachments, or via overnight courier.

Reporting to FDA: In agreement with the IND regulations, the investigators will report SAEs/Unexpected AEs to the FDA as well as the Program Officer at NIAAA:

